### **12.3 Stratification Factors**

First-line metastatic treatment versus 2nd-line and beyond. We will enroll 14 patients who have not received prior cytotoxic chemotherapy in the metastatic setting, and 14 patients who have received prior cytotoxic chemotherapy.

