Primary Endpoint(s): objective radiographic response rate (ORR), as defined by RECIST v1.1.
Secondary Endpoint(s): 

1. progression free survival

2. overall survival

3. duration of response

4. time to treatment failure

5. adverse effects

Study Design: Single arm phase II study. Patients will receive modified FOLFIRINOX which consists of 85 mg/m  of oxaliplatin, 400 mg/m  of leucovorin over the first 2 hours, 165 mg/m  of irinotecan in a 90-minute infusion on day 1, followed by a continuous, 46-hour infusion of 5-FU at a dosage of 2,400 mg/m  . A cycle will be repeated every 14 days. G-CSF prophylaxis will be allowed after each cycle. Patients will undergo re-staging studies every 8 weeks. Patients will receive up to 12 cycles during the study. Additional cycles will be determined per investigators' discretion.
Number of Patients: 28 evaluable patients split evenly between 1 st line cytotoxic treatment and ≥2 nd line treatment

**Main Criteria for Inclusion/Exclusion:**Inclusion criteria:

- Cytologically or histologically confirmed high grade neuroendocrine carcinoma of gastrointestinal tract (including pancreas). Patients with unknown origin for the neuroendocrine carcinoma in which a gastrointestinal origin is suspected (per pathologist or investigator's discretion) will be eligible for the study
- Tumors must have a Ki-67 index greater than 20% and/or >20 mitotic figures/10 high-power fields.
- Patient must have metastatic disease.
- Patients must measurable disease, as defined by RECIST 1.1 criteria.
- Any line of treatment (first line versus beyond first line)
- Age  $\geq$ 18 years
- Eastern Cooperative Oncology Group performance status of 0,1 or 2 (see appendix A)
- Patients must have adequate hepatic, renal and hematological functions. See protocol for details.
- Ability to understand and willingness to sign a written informed consent

document Main Exclusion criteria:

- Prior treatment with 5-FU, leucovorin, irinotecan and/or oxaliplatin
- Patients with a secondary primary cancer (excluding skin non-melanomatous) within 1 year of the diagnosis of neuroendocrine carcinoma
- Patients with childbearing potential who are not willing to use adequate contraception precautions during the study and for 3 months after stopping study chemotherapy

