## **3. STUDY DESIGN**

This is a prospective phase II open-label trial, stratifying gastroenteropancreatic high grade neuroendocrine carcinomas patients equally into two cohorts (first-line versus beyond first-line).

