### **12.2 Sample Size/Accrual Rate**

For our primary endpoint, based on historical data and taking into account a mixed population of first-line versus beyond-first-line treatment patient population, we estimate response rate of 30% with standard platinum-based chemotherapy ( $H_0:p=0.30$ ). We hypothesize that FOLFIRINOX will have a response rate of 50% ( $H_1:p=0.50$ ). Using an alpha error of 0.10 and a beta error (1 minus power) of 0.20, based on the Simon two stage design, we estimate that we will need 28 evaluable patients to complete this trial. For the stage 1 part of this trial, 12 patients will be enrolled. If 3 or fewer patients achieve ORR, the trial will be stopped. If 4 or more patients achieve ORR, another 16 patients will be enrolled. By the end of the trial, if 11 or fewer patients achieve ORR, this trial will be considered a failure and no further investigation is warranted. We estimate that accrual will take 2 to 3 years. Primary objective will be evaluated after stage 1 and after stage 2, once the sample size is achieved. Patients who consent for the trial but do not receive any dose of treatment will be considered dropouts and will be replaced.

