### **12.4 Analysis of Endpoints**

- a) Response rates defined by RECIST criteria, version 1.1. Best response rates to treatment will be summarized in 4 ordinal categories: complete response, partial response, stable disease or progression of disease.
- b) Data on progression-free survival (initiation date of therapy to disease progression or death) and overall survival (initiation date of therapy to death) will be collected. Patients alive and free of progression by the time of analysis will be censored and patients who progress or died will be classified as “failures” for statistical analysis purpose. Kaplan-Meier methodology will be used to summarize time-to-event variables.
- c) Safety analysis will be analyzed by collecting date on treatment-related morbidity and mortality. We will collect data on frequency, type and severity of all adverse events that occur on or after Cycle 1, Day 1 according to National Cancer Institute Common Toxicity Criteria for Adverse Events (NCI CTCAE; Version 4.0). Results will be presented as a table.

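### Should section 12.4 have to specify response, PFS and OS by line of therapy, given that the trial enrols two fixed cohorts of 14?

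*Combined protocol and SAP*

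**What the plan says.** The split by line of therapy appears in three places. The synopsis gives the sample as "28 evaluable patients split evenly between" first-line and later-line treatment. Section 3 describes stratifying "carcinomas patients equally into two cohorts (first-line versus beyond first-line"). Section 12.3, headed as the stratification factors, fixes the numbers: "14 patients who have not received prior cytotoxic chemotherapy in the metastatic setting, and 14 patients who have received prior cytotoxic chemotherapy".

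The hypothesis is pooled. Section 12.2 sets a 30% null response rate, "taking into account a mixed population of first-line versus beyond-first-line treatment patient population", against a 50% alternative, with alpha 0.10 and beta 0.20. The rule has two steps. The first is "For the stage 1 part of this trial, 12 patients will be enrolled" and "If 3 or fewer patients achieve ORR, the trial will be stopped". The second, at 28 patients, is that "if 11 or fewer patients achieve ORR, this trial will be considered a failure and no further investigation is warranted".

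Section 12.4 covers the analyses: "Best response rates to treatment will be summarized in 4 ordinal categories: complete response, partial response, stable disease or progression of disease", Kaplan-Meier summaries of the time-to-event variables, and a table of adverse events. None is described by cohort, and none is described as pooled only. The endpoint list in section 2 and the response and time-to-event definitions in section 11 add nothing by line.

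**The concern.** In a single-arm trial, stratification balances no treatment arms. If the protocol takes the trouble to fill two quotas of 14, the obvious analytic use is to show results for each, and section 12.4 does not say that this will be done. The background also treats the two settings differently: section 1.2 describes guideline support for platinum with etoposide in advanced disease and no consensus on second-line therapy.

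At stake is how a pooled result is read. The smallest success, 12/28, is compatible with equal activity in both lines (6/14 and 6/14) or with activity concentrated in one (10/14 and 2/14), and no written requirement makes the report distinguish them. If a breakdown were chosen only after the data were seen, a reader might discount it as a post hoc subgroup.

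**Working it through.** **Step 1: reproduce the plan's figure.** Inputs from section 12.2: p0 = 0.30, p1 = 0.50, 12 patients in stage 1, stop at 3 or fewer responders, 16 more patients, failure at 11 or fewer of 28. The probability of declaring success at response rate p is

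P(success) = Σ over x from 4 to 12 of P(X1 = x) × P(X2 ≥ 12 − x), with X1 ~ Bin(12, p) and X2 ~ Bin(16, p).

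- At p = 0.30 the terms for x = 4, 5, 6, … are 0.2311 × 0.0744 + 0.1585 × 0.1753 + 0.0792 × 0.3402 + 0.0291 × 0.5501 + 0.0078 × 0.7541 + … = 0.0954. The chance of stopping after stage 1 is 0.493.
- At p = 0.50 the same sum is 0.8020. The chance of stopping after stage 1 is 0.073.

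A search over all two-stage designs with alpha ≤ 0.10 and power ≥ 0.80 returns this one as the minimax design. The stated 28 and both boundaries are right. When both lines share one response rate, these figures do not depend on how many first-line patients fall in stage 1.

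**Step 2: does pooling hide something the tables would reveal?** The documents give no FOLFIRINOX response rate by line, so the true rates here are assumptions. The calculation is an exact convolution of two binomials, 14 per cohort, with 6 + 6 in stage 1. Each range covers all 13 possible stage 1 mixes.

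| True rates by line | P(pooled success) | P(gap ≥ 4 responders given success) | P(gap ≥ 8 given success), 6 + 6 only |
|---|---|---|---|
| 50% / 50% | 0.802 | 0.19 (0.17 to 0.19) | 0.004 |
| 50% / 30% | 0.425 (0.337 to 0.446) | 0.45 (0.29 to 0.46) | 0.04 |
| 60% / 30% | 0.643 (0.438 to 0.667) | 0.65 (0.48 to 0.65) | 0.11 |

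The success probabilities describe the pooled rule. They stay the same whether or not cohort tables are printed, so they do not measure any harm from leaving the tables out of section 12.4. The gap columns do bear on the tables. A gap of 4 or more is commoner when the lines truly differ, but it still occurs in 19% of successes when they do not. The 10/14 + 2/14 example is a gap of 8. Gaps that large make up 0.4% of successes at equal 50% rates, 4% at 50%/30% and 11% at 60%/30%.

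**Step 3: what could a cohort table support?** Exact (Clopper-Pearson) 95% intervals, not adjusted for the two stages:

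- pooled 12/28: 24.5% to 62.8%
- 10/14: 41.9% to 91.6%
- 2/14: 1.8% to 42.8%
- 6/14: 17.7% to 71.1%
- 7/14: 23.0% to 77.0%, a width of 77.0 − 23.0 = 54 points
- 4/14: 8.4% to 58.1%, a width of 58.1 − 8.4 = 49.7 points

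Even 10/14 and 2/14 have intervals that overlap slightly (41.9% against 42.8%).

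A 30% versus 50% test within one cohort of 14 cannot meet the plan's error rates. Requiring 7 or more responders gives alpha 0.093 and power 0.605; requiring 6 or more gives alpha 0.219 and power 0.788. Comparing the cohorts with each other (30% against 50%, two-sided 0.05) has about 18% power. Cohort results could therefore be estimates only, with no claim attached.

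**The case for a change.** The best argument for a change is that the addition is free. Line of therapy is recorded at entry, the tables need no extra patients, visits or alpha, and a sentence written beforehand separates a prespecified description from a subgroup picked afterwards. If the regimen reached the plan's own 50% target in one line while the other stayed at 30%, the trial would still pass about 43% of the time, and readers would want to know which line responded.

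Part of this stands: section 12.4 does not state a breakdown, and stating it would be tidy. The rest carries less weight. The partition is already fixed before any data, with its size, in sections 3 and 12.3, so a later table by line would not be a data-driven choice of subgroup. The 43% figure belongs to the pooled design, which is correct for the mixed population that section 12.2 defines, and added tables leave it unchanged. Any sensible wording would also keep 12/28 as the only decision rule and bar separate cohort claims, so the verdict would still be drawn for both lines together.

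The documents do not settle whether the lines differ. Section 1.2 quotes 31% with platinum/etoposide and 29% with FOLFOX after cisplatin failure, both close to the pooled null, but also 42% to 67% with cisplatin/etoposide in other series.

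**Conclusion.** No change to the plan is needed. Followed as written, it gives a valid pooled estimate and a valid decision for an evenly mixed first-line and later-line population, with exact alpha 0.095 and power 0.802 against targets of 0.10 and 0.80. What is left open is a reporting detail: whether response, progression-free survival and overall survival are also displayed for each cohort. An analyst who finds line of therapy listed as the stratification factor would ordinarily fill that gap, using the cohort sizes actually enrolled, including after an early stop. The gain from writing it down is zero in sample size, boundaries, error rates and decisions. The tables would carry intervals about 50 points wide.

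This rests on two readings: that section 12.4 is silent on cohorts and does not exclude them, and that the pooled 12/28 rule is the trial's only decision rule, as section 12.2 has it. It does not rest on the assumed rates by line, since no choice of those rates makes a descriptive table alter the decision.

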### **12.4 Analysis of Endpoints**

- a) Response rates defined by RECIST criteria, version 1.1. Best response rates to treatment will be summarized in 4 ordinal categories: complete response, partial response, stable disease or progression of disease.
- b) Data on progression-free survival (initiation date of therapy to disease progression or death) and overall survival (initiation date of therapy to death) will be collected. Patients alive and free of progression by the time of analysis will be censored and patients who progress or died will be classified as “failures” for statistical analysis purpose. Kaplan-Meier methodology will be used to summarize time-to-event variables.
- c) Safety analysis will be analyzed by collecting date on treatment-related morbidity and mortality. We will collect data on frequency, type and severity of all adverse events that occur on or after Cycle 1, Day 1 according to National Cancer Institute Common Toxicity Criteria for Adverse Events (NCI CTCAE; Version 4.0). Results will be presented as a table.

### **12.5 Replacement of Dropouts**

Patients who enroll but do not receive the initial cycle of FOLFIRINOX will be considered dropouts and will be replaced.

## **13. DATA COLECTION**

Once eligibility has been established and the participant successfully registered, the participant is assigned a protocol case number. This number is unique to the participant on this trial and must be used for case report form (CRF) completion in Oncore.

Data Managers must enter the information required by the protocol onto CRFs.

## **14. REGULATORY CONSIDERATIONS**

### **14.1 Protocol review and amendments**

This protocol, the proposed informed consent and all forms of participant information related to the study (e.g., advertisements used to recruit participants) and any other necessary documents must be submitted, reviewed and approved by a properly constituted IRB governing the study location.

Any change or addition (excluding administrative) to the study protocol or informed consent form protocol must be submitted as amendments and must be reviewed and approved by Pharmacyclics and the investigator before implementation. Amendments significantly affecting the safety of subjects, the scope of the investigation or the scientific quality of the study require additional approval by the IRB. Any changes in study conduct must be reported to the IRB. The Principal Investigator will disseminate protocol amendment information to all participating investigators.

All decisions of the IRB concerning the conduct of the study must be made in writing.

### **14.2 Informed consent**

The investigator must explain to each subject (or legally authorized representative) the nature of the study, its purpose, the procedures involved, the expected duration, the potential risks and benefits involved and any discomfort it may entail. Each subject must be informed that participation in the study is voluntary and that he/she may withdraw from the study at any time and that withdrawal of consent will not affect his/her subsequent medical treatment or relationship with the treating physician.

This informed consent should be given by means of a standard written statement, written in non-technical language. The subject should read and consider the statement before signing and dating it, and should be given a copy of the signed document. If the subject cannot read or sign the documents, oral presentation may be made or signature given by the subject's legally appointed representative, if witnessed by a person not involved in the study, mentioning that the patient could not read or sign the documents. No patient can enter the study before his/her informed consent has been obtained.

The informed consent form is considered to be part of the protocol, and must be submitted by the investigator with it for IRB approval. The original signed copy of the consent document must be retained in the medical record or research file.

### **14.3 Committees**

#### **14.3.1 Scientific Review Committee (SRC)**

Each SRC conducts a formal internal peer review of all clinical protocols and general scientific oversight of interventional clinical research. Protocols are reviewed for scientific merit, adequate study design, safety, availability of targeted study population, and feasibility of timely completion of all proposed research projects to be conducted by its assigned programs at the Cancer Center. Each SRC is responsible for evaluation the risk/benefit assessment and corresponding data and safety monitoring plan as part of the scientific review and approval process.

#### **14.3.2 Data Safety Monitoring Committee (DSMC)**

The DSMC will meet on a monthly basis and will continually assess for subject safety and recommend changes to protocol and study as required to preserve subject safety and prevent any untoward toxicity.

#### **14.3.3 Protocol monitoring Committee (PMC)**

This study will be reviewed by the PMC for data and safety monitoring. The PMC monitors its assigned ongoing research protocol for: serious adverse event reporting, data and safety monitoring, and internal audit findings. The PMC, upon review of any agenda item, may approve the study for continuation, require revisions, suspend or close a protocol.

#### **14.4 Internal monitoring**

The trial will be monitored per Moffitt Cancer Center policy MRI-P.PSO.03, *Monitoring of Investigator Initiated Clinical Research*. Data will be captured in Oncore, Moffitt's Clinical Trials Database, Regulatory documents and case report forms will be monitored internally according to Moffitt Cancer Center Monitoring Policies. Monitoring will be performed regularly to verify data is accurate, complete and verifiable from source documents; and the conduct of the trial is in compliance with the currently approved protocol/amendments, Good Clinical Practice, and applicable regulatory requirements.

#### **14.5 Ethics and Good Clinical Practice (GCP)**

It is the responsibility of the investigator to have prospective approval of the trial protocol, protocol amendments, informed consent forms, and other relevant documents, e.g., advertisements, if applicable, from the IRB/IEC. The trial will be performed in accordance with the protocol, International Conference on Harmonization Good Clinical Practice guidelines, and applicable local regulatory requirements and laws.

It is understood that deviations from the protocol should be avoided, except when necessary to eliminate an immediate hazard to a research participant. In such case, the deviation must be reported to the IRB according to the local reporting policy.

#### **14.6 Declaration of Helsinki**

The investigator must conduct the trial in accordance with the principles of the Declaration of Helsinki. Copies of the Declaration of Helsinki and amendments will be provided upon request or can be accessed via the website of the World Medical Association at [http://www.wma.net/e/policy/17-c\\_e.html](http://www.wma.net/e/policy/17-c_e.html).

#### **14.7 Study documentation**

The investigator must prepare and maintain adequate and accurate case histories designed to record all observations and other data pertinent to the study for each research participant. This information enables the study to be fully documented and the study data to be subsequently verified.

Original source documents supporting entries in the case report forms include but are not limited to hospital records, clinical charts, laboratory and pharmacy records, recorded data from automated instruments, microfiches, photographic negatives, microfilm or magnetic media, and/or x-rays.

#### **14.8 Retention of records**

Retained records will include all documentation of adverse events, records of study drug receipt and dispensation, and all IRB correspondence for at least 5 years after the investigation is completed.

**APPENDIX A**  
**Performance Status Criteria**

ECOG Performance Status Scale		Karnofsky Performance Scale	
Grade	Descriptions	Percent	Description
0	Normal activity. Fully active, able to carry on all pre-disease performance without restriction.	100	Normal, no complaints, no evidence of disease.
		90	Able to carry on normal activity; minor signs or symptoms of disease.
1	Symptoms, but ambulatory. Restricted in physically strenuous activity, but ambulatory and able to carry out work of a light or sedentary nature (e.g., light housework, office work).	80	Normal activity with effort; some signs or symptoms of disease.
		70	Cares for self, unable to carry on normal activity or to do active work.
2	In bed <50% of the time. Ambulatory and capable of all self-care, but unable to carry out any work activities. Up and about more than 50% of waking hours.	60	Requires occasional assistance, but is able to care for most of his/her needs.
		50	Requires considerable assistance and frequent medical care.
3	In bed >50% of the time. Capable of only limited self-care, confined to bed or chair more than 50% of waking hours.	40	Disabled, requires special care and assistance.
		30	Severely disabled, hospitalization indicated. Death not imminent.
4	100% bedridden. Completely disabled. Cannot carry on any self-care. Totally confined to bed or chair.	20	Very sick, hospitalization indicated. Death not imminent.
		10	Moribund, fatal processes progressing rapidly.
5	Dead.	0	Dead.

## APPENDIX B

### Cytochrome P450 Enzymes Involved in Drug Metabolism: Substrates, Inducers, and Inhibitors

Isozyme	Substrates	Inhibitors	Inducers
CYP1A2	Clozapine Cyclobenzaprine Fluvoxamine Imipramine Mexiletine Propranolol Theophylline	Cimetidine Ciprofloxacin Clarithromycin Enoxacin Erythromycin Fluvoxamine Ofloxacin Ticlopidine	Polycyclic Aromatic Hydrocarbons (Cigarette Smoke) TCDD (dioxin)
CYP2C9	Diclofenac Flurbiprofen Ibuprofen Losartan (not candesartan or telmisartan) Naproxen Phenytoin Piroxicam Sulfamethoxazole Tolbutamide Warfarin	Amiodarone Fluconazole Fluoxetine Isoniazid Paroxetine Ticlopidine Zafirlukast	Phenobarbital Rifampin
CYP2C19	Amitriptyline Clomipramine Cyclophosphamide Diazepam Imipramine Lansoprazole Nelfinavir Omeprazole Phenytoin	Cimetidine Fluoxetine Fluvoxamine Ketoconazole Lansoprazole Omeprazole Paroxetine Ticlopidine	Carbamazepine Norethindrone
CYP2D6	Amitriptyline Clomipramine Codeine Desipramine Dextromethorphan Imipramine Metoprolol Nortriptyline Oxycodone Paroxetine Propranolol Risperidone Thioridazine Timolol	Amiodarone Fluoxetine Haloperidol Indinavir Paroxetine Quinidine Ritonavir Sertraline	Rifampin
CYP2E1	Acetaminophen Chlorzoxazone Ethanol Enflurane Halothane Isoflurane	Disulfiram	Chronic Ethanol Isoniazid
CYP3A	Alprazolam Astemizole Buspirone Calcium Channel Blockers Carbamazepine Cisapride Cyclosporine Protease Inhibitors Lovastatin Midazolam Simvastatin Tacrolimus Triazolam	Amiodarone Cimetidine Clarithromycin Erythromycin Grapefruit Juice Itraconazole Ketoconazole	Carbamazepine Glucocorticoids Phenytoin Rifampin Ritonavir
